#### **4. SAMPLE SIZE DETERMINATION AND POWER**

In the MINT pilot trial, the composite 30-day rate of death and myocardial infarction was 16.4%. Using a two-sided inequality test and a simple chi-square statistic with  $\alpha=0.05$ , we determined the sample sizes required to provide 80% and 90% power to detect varying relative reductions in the 30-day event rates for death and myocardial infarction between the two assigned treatment groups. Based on these estimates, we planned to enroll a sample of 3500 patients. If the rate of missing outcome data were  $\leq 5\%$ , the trial would have 3324 patients with analyzable outcome data at 30-days. Assuming an overall event rate of 16.4%, the trial would have 80% power to detect a 20% relative reduction (i.e. 18.2% vs. 14.6%) and >90% power to detect a 25% relative reduction.

## **5. INTERIM MONITORING PLAN**

The DSMB reviews interim analyses of the outcomes by assigned treatment group on an annual basis (from July 2018 through July 2022). The interim monitoring is designed to test for evidence of beneficial effect with either treatment strategy while maintaining the overall type I error at the pre-specified level. Stopping rules are based on the information (i.e. number of primary outcome events that have accumulated) at each inspection time and the shape of the predetermined alpha-spending function. The Lan-DeMets approach was used to allocate the type 1 error (i.e. alpha-level) at each interim time point and use of O'Brien Fleming monitoring boundaries. The DSMB will use the monitoring information to determine its recommendation to NHLBI. The DSMB may advise early termination of the trial for safety reasons or make other recommendations regarding modifications to the protocol. The final decision to stop the trial rests with the NHLBI. If the recommendation is to stop the trial, the MINT trial principal investigators are to be consulted before a final decision is made.

In order to ensure that the MINT trial has adequate power, an interim analysis to assess sample size was planned when approximately half of the participants are projected to have completed the 30-day follow-up. Revised sample size estimates were to be calculated based on the original power and effect size estimates from the trial hypothesis (80% power to detect a RR=0.80) and on the observed overall event rate (i.e. the two transfusion groups combined). The DSMB was to evaluate whether the trial sample size needs to be increased in order to restore power to maintain the ability to detect a clinically meaningful effect size. The DSMB reviewed this analysis at the January 2020 meeting. At that point, 1078 participants had finished 30-days follow-up plus an additional 6 months to ensure that all adjudication materials for the primary outcome were completed. Based on the results of this analysis, the DSMB voted to continue the MINT trial without any modification to the planned sample size (N=3500).

The original Data Safety Monitoring Plan stated that no interim futility analyses would be conducted since the MINT trial compares two established transfusion strategies with different resource and cost implications, and hence, a null result from a well-powered trial would be important for establishing treatment guidelines and policy. The study team submitted an application for additional trial funding to the NHLBI; in response, the NHLBI requested a futility analysis in February 2022. The study team submitted a conditional power plan in April 2022, and this plan was approved by a blinded statistical team at NHLBI in May 2022. The plan and results were presented to the DSMB on July 22, 2022.

The MINT interim monitoring plan included a tiered approach for determining the continuation of the MINT trial. First, the efficacy monitoring that has occurred annually since the beginning of the trial will be

performed to test if one arm is statistically superior to the other arm. Next, if superiority is not detected, then a futility analysis will occur. To determine futility, the conditional power for superiority of either arm with respect to the primary outcome will be performed assuming that the future trend is either consistent with the current trend (i.e. the maximum likelihood estimate), with the null hypothesis, with the alternative hypothesis favoring the restrictive strategy, and with the alternative hypothesis favoring the liberal strategy. If the conditional power of ANY of these tests is  $> 20\%$ , then we recommend the study continue. If the conditional power of ALL of the specified tests for superiority are  $\leq 20\%$ , then we recommend moving to the non-inferiority testing. The conditional power for non-inferiority of the restrictive arm (compared to the liberal arm) will be performed assuming a relative 15% margin of non-inferiority (i.e. risk ratio for Restrictive versus Liberal  $< 1.15$ ) and that the future trend is consistent with either the current trend (i.e. the maximum likelihood estimate), with the null hypothesis, with the alternative hypothesis favoring the restrictive strategy, and with the alternative hypothesis favoring the liberal strategy. If the conditional power of ANY of the non-inferiority conditional power tests is  $> 20\%$ , then we recommend the study continue. If the conditional power of ALL the specified tests for non-inferiority are  $\leq 20\%$ , then termination of trial enrollment would be considered. Based on the results of this analysis, the DSMB voted that the MINT trial continue to the planned sample size (N=3500).

## **6. ANALYTIC APPROACH**

### **CONSORT Chart**

A CONSORT chart will be created to describe the flow of all participants who were consented to participate in the MINT trial through 180-days of follow-up. See Figure 1 as an example in the Supplement to this document.

### **Baseline Characteristics of the Enrolled Patient Sample**

The baseline characteristics and co-interventions of the patients randomized in the trial will be described using frequencies, proportions, means and standard deviations, or medians and first and third quartiles. Characteristics will be presented for the entire sample and stratified by treatment assignment. See Table 1 in the Supplement for an example.

### **Adherence to Assigned Intervention**

The distribution of the number of red blood cell units transfused per participant will be described for each randomized treatment group (e.g. Figure 2a). The counts and mean number of units per participant as

well as the total number of transfused units will be described, and the mean number of transfused units will be compared between assigned transfusion strategy groups using a simple Poisson test.

The mean hemoglobin concentration at Baseline, 1, 2, and 3 days post-randomization will be compared graphically between the assigned treatment groups for all randomized patients (e.g. Figure 2b). Linear mixed effect models will be used to compare the daily mean hemoglobin concentrations on day 1, 2 and 3 post-randomization by assigned treatment group adjusting for the baseline hemoglobin value and accounting for the repeated measures per participant using a random intercept.

$$\text{Post-rand Hgb}_{ij} = \beta_0 + \beta_1 \text{Restrictive}_j + \beta_2 \text{Day}_{jj} + \beta_3 \text{Restrictive}_j * \text{Day}_{ij} + \beta_4 \text{Baseline Hgb}_i + \alpha_i + \epsilon_{ij}$$

where  $i$ =participant,  $j$ = day 1, 2 or 3,

Restrictive = 1 for assigned to Restrictive and 0 for assigned to Liberal;

Day is categorical Day1, Day 2, Day 3;

$\alpha_i$  is a random intercept for participant  $i$ .

All patients with at least one non-missing in-hospital hemoglobin value on day 1, 2, or 3 will be included in the analysis. If the interaction is not statistically significant ( $p > 0.05$ ) it will be removed from the model. The estimated beta coefficients for Restrictive (versus Liberal) strategy and for the interaction between Restrictive strategy and Day will be presented along with their 95% confidence intervals and p-values. Contrasts will be created from this model to display the estimated difference in hemoglobin levels between the Restrictive and the Liberal groups on Day 1, Day 2 and Day 3.

We will also quantify adherence to the protocol by presenting the following among all randomized patients. For those assigned to Restrictive strategy, we will report the number (%) of randomized patients with at least one transfusion given when  $\text{Hgb} > 8$ , and the number (%) of patients with at least one transfusion when no hemoglobin level was checked. Clinical reasons will be provided when possible. For those assigned to Liberal strategy, we will present the number (%) of randomized patients with no transfusion, and the number (%) of patients where the last hemoglobin value before hospital discharge is  $< 10$  g/dL. Clinical reasons will be provided when possible. Among all randomized patients, we will present the number (%) of patients with one and with two or more missing required hemoglobin measures, and number (%) of patients with one and with two or more missing troponin measures.

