Systematic Reviews, Observational Studies: We have identified or conducted systematic reviews of both observational studies and clinical trials. As expected, a systematic review of observational studies in all patients found that blood transfusion was associated with increased mortality and morbidity.(27) Two recent systematic reviews focusing specifically on patients with myocardial infarction identified 10 studies (9 observational and 1 pilot trial) reporting the effects of transfusions on mortality.(28, 29) Nearly all observational studies demonstrated an association between transfusion and higher mortality. The one exception was in a large study using Medicare billing data in 79,000 patients with acute myocardial infarction.(30) Transfusion was associated with a lower risk of death when patients had an admission hematocrit below 0.33 (equal to a hemoglobin concentration of 11 g/dL) (odds ratio= 0.69; 95% CI, 0.53-0.89) and relationship between transfusion and better outcomes increased as the hematocrit fell. Indeed, based on subgroup analyses, the authors of the systematic review report that the adverse effects of transfusion appear to be mitigated in patients with a hematocrit less than 0.33. Unfortunately, observational studies cannot be used to evaluate the effect of red blood cell transfusion since the use of blood transfusion is a marker for illness burden. (29, 31) Thus, no matter how refined the adjustment is for differences in illness burden, it is difficult, if not impossible, to completely adjust for differences between patients receiving and not receiving blood transfusion.

Systematic Reviews, Clinical Trials: We have performed a systematic review of clinical trials evaluating transfusion triggers in a variety of populations that were published in the Cochrane database(32) and JAMA.(33) We have updated the review (34) and found that compared with higher hemoglobin transfusion thresholds (~10 g/dL), a hemoglobin transfusion threshold of 7 or 8 g/dL is associated with fewer red blood cell units transfused (mean difference, -1.22 units per patient), without adverse associations with mortality, cardiac morbidity, functional recovery, or length of hospital stay. The relative risk for the association of restrictive versus liberal transfusion on 30-day all-cause mortality was 0.99 (95% CI, 0.82 to 1.20).

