The mean hemoglobin concentration at 1, 2, and 3 days post-randomization will be compared between the assigned treatment groups with a Student's t-test. Mixed random effect models will be used to describe the daily mean hemoglobin concentrations during the initial hospitalization following randomization and to compare these repeated measures by assigned treatment group. The mean number of red blood cell transfusions in each randomized treatment group will be described, and a simple Poisson test will be used to test whether the number of units of blood differs significantly by assigned transfusion strategy.

4.c Primary Outcome Analysis

The intention-to-treat principle will be used for all randomized transfusion strategy comparisons of study outcomes. A two-sided test will be used with an alpha-level=0.05 for the primary outcome, the composite of all-cause mortality and myocardial infarction (death/MI) by 30 days from randomization. The 30-day event rate for the primary outcome will be compared by assigned transfusion strategy using an unadjusted log-binomial regression model with a fixed effect variable for assigned treatment strategy and a random effect for clinical site. The primary analysis will involve the estimated relative risk and significance level obtained from the model accounting for interim monitoring and missing data. Event rates, the relative risk and the absolute difference will be from the observed data will also be presented, and 95% confidence intervals will be calculated.

If significant imbalances in baseline risk factors are detected between the two randomized treatment groups (p<0.05), multivariable log-binomial regression will be used to adjust for potential confounding factors as a sensitivity analysis. If adherence to the protocol is lower than expected, a per protocol analysis, including only patients who undergo transfusion according to their assignment and adjusting for baseline factors that are associated with adherence to the treatment protocol, will be conducted as a sensitivity analysis.

4.d Analysis of Secondary and Tertiary Outcomes

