## **Trial Transfusion Strategies**

The trial compares a restrictive and a liberal approach to transfusion therapy. The transfusion strategy is followed during the index hospitalization from the time of randomization up to 30-days post-randomization, hospital discharge, or death, whichever comes first.

Restrictive Transfusion Strategy: Patients randomized to the restrictive transfusion strategy may receive a transfusion if the hemoglobin concentration falls below 8 g/dL and are strongly encouraged to receive transfusion if the hemoglobin concentration is below 7 g/dL. Transfusion is also allowed when anginal symptoms are determined by the patient's treating physician to be related to anemia and are not controlled with anti-anginal medications. Enough blood is given to increase the hemoglobin concentration to above 7 to 8 g/dL or to relieve anginal symptoms. A post transfusion hemoglobin measurement is required.

Liberal Transfusion Strategy: Patients randomly allocated to the liberal transfusion strategy receive one unit of packed RBCs following randomization and will receive enough blood to raise the hemoglobin concentration to 10 g/dL or above any time during the index hospitalization that the hemoglobin concentration is detected to be below 10 g/dL. A post transfusion hemoglobin measurement showing a hemoglobin level of at least 10 g/dL must be obtained.

For both strategies, blood is administered one unit at a time followed by a hemoglobin measurement. A patient in either group may be transfused at any time without a hemoglobin level if the patient is actively bleeding (e.g., brisk gastrointestinal bleeding) and the treating physician believes an emergency transfusion is needed. A patient in either group with history of congestive heart failure or low ejection fraction may receive diuretics prior to or after transfusion and transfusion may be delayed until the patient can safely tolerate the additional volume. Patients with end stage renal disease may receive transfusion during dialysis if requested by treating physician. The transfusion protocol is suspended for 24 hours if the patient goes to surgery.

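### Minor: the simple Poisson test for red cell units per patient fixes the variance at the mean, which the transfusion rules make doubtful in both arms, so its p-value may be too small or too large

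*SAP*

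**What the plan says.** Under Adherence to Assigned Intervention, SAP section 6 states that "the mean number of transfused units will be compared between assigned transfusion strategy groups using a simple Poisson test". Protocol F4 4.b makes the same choice as an explicit significance test: "a simple Poisson test will be used to test whether the number of units of blood differs significantly by assigned transfusion strategy". Neither document adds a dispersion check, a robust variance, a negative binomial model or a nonparametric fallback.

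The SAP surrounds the test with description: "The distribution of the number of red blood cell units transfused per participant will be described for each randomized treatment group" (Figure 2a), together with counts, means and total units. No confidence interval is planned for units, and template Tables 2 and 3 have no row for them.

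The rules that generate the counts are in SAP section 1, Trial Transfusion Strategies. In both arms, "blood is administered one unit at a time followed by a hemoglobin measurement". Liberal patients "receive one unit of packed RBCs following randomization and will receive enough blood to raise the hemoglobin concentration to 10 g/dL or above". Restrictive patients "may receive a transfusion if the hemoglobin concentration falls below 8 g/dL", or for angina attributed to anemia that medication does not control. Either arm may be transfused without a hemoglobin value during active bleeding.

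**The concern.** A simple Poisson comparison gets its standard error from the means alone. It is calibrated only if the variance of units per patient is close to the mean, and the rules push the variance away from the mean in both directions.

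- **Liberal arm.** The protocol unit raises the mean but adds almost no variance, and stopping at a target limits the spread. Both favor underdispersion, although bleeding can reverse it.
- **Restrictive arm.** Many patients may never reach the lower threshold and will have zero units, while a few who bleed may receive many. That favors overdispersion.

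The p-value for units, and the width of any interval taken from the same model, are what is at stake. This is the plan's only formal test of blood use. The Protocol describes red cells as scarce and costly, and it justifies the value of a null result partly by the strategies' different resource implications. Readers are therefore likely to use the number of units saved, and its precision should be sound.

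**Working it through.** The documents give no mean, SD, dispersion or p-value for units, so the plan has no figure of its own to reproduce.

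**Inputs**
- 3500 patients allocated 1:1, so 1750 per arm (SAP sections 1 and 4).
- Two-sided 5% level. The SAP states this for the trial aims and states none for the adherence comparison, so its use here is an assumption.
- A difference of 1.22 units per patient. This comes from other trials (Protocol background, review of clinical trials) and is not a design input.
- φ, the variance/mean ratio of units per patient: assumed, with a range shown. For the two arms together, φ = (var_R + var_L)/(mean_R + mean_L).

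**Step 1. Calibration.** The true size of a nominal 5% Poisson test is 2·(1 − Φ(1.96/√φ)). The ratio of true to Poisson standard error is √φ.

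| Assumed φ | √φ | True size |
|---|---|---|
| 0.5 | 0.71 | 0.6% |
| 0.75 | 0.87 | 2.4% |
| 1 | 1.00 | 5.0% |
| 1.5 | 1.22 | 11.0% |
| 2 | 1.41 | 16.6% |
| 3 | 1.73 | 25.8% |

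Simulated negative binomial counts (1750 per arm, 2000 trials per setting, means of 1 and 2) agree: 17% to 18% at φ = 2. A z-test with empirical variances held 4.4% to 6.1% at every φ from 1 to 4.

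**Step 2. Direction, with two assumed arms.**
- Restrictive: 65% zeros and a mean of 2 among those transfused, so the mean is 0.35 × 2 = 0.70. If the positive counts are geometric, the variance is 0.35 × 6 − 0.49 = 1.61 (φ = 2.3). If they are 1 + Poisson(1), it is 0.35 × 5 − 0.49 = 1.26 (φ = 1.8). If they are exactly two units each, it is 0.35 × 4 − 0.49 = 0.91 (φ = 1.3).
- Liberal: 1 + Poisson(1.5), so the mean is 2.5 and the variance 1.5 (φ = 0.6).

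On the difference scale the Poisson variance is proportional to 0.70 + 2.50 = 3.20. The true variance is 1.61 + 1.50 = 3.11, 1.26 + 1.50 = 2.76 or 0.91 + 1.50 = 2.41, giving ratios of 0.97, 0.86 and 0.75. The test is then about right or somewhat conservative.

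On the log rate-ratio scale, for the geometric case, the true variance is proportional to 2.3/0.70 + 0.6/2.50 = 3.53, against a Poisson value of 1/0.70 + 1/2.50 = 1.83. The ratio is 1.9, so a Poisson interval would be too narrow.

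**Step 3. A give-to-target simulation.** All inputs are assumed: baseline hemoglobin centered at 8.6 g/dL, about 1 g/dL gained per unit, and daily losses and the share of bleeders rising across scenarios.

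| Share bleeding | φ liberal | φ restrictive | z Poisson | z robust |
|---|---|---|---|---|
| 0% | 0.35 | 1.1 | 53 | 81 |
| 10% | 0.75 | 2.1 | 46.9 | 46.6 |
| 20% | 1.6 | 3.6 | 42 | 29 |

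The Poisson z is too small, about right and too large in turn.

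**Step 4. Would the finding of a difference change?** z = 1.22/√((m_R + m_L)/1750), with m_L = m_R + 1.22. For an assumed m_R of 0.3 to 3 units, z runs from 37.8 down to 19.0. At φ = 4 these halve to 18.9 and 9.5. Significance is lost only when φ exceeds (z/1.96)², about 373 down to 94. A small difference could flip: 0.10 units at a mean near 2 gives z = 0.10/√(4/1750) = 2.09 under Poisson and 2.09/√2 = 1.48 at φ = 2.

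**The case against.** The strongest reply is that the test cannot mislead anyone. The arms differ by design, so equal means is not a realistic null hypothesis and a table of true sizes is largely academic. At a difference like that seen in other trials, no plausible dispersion removes significance. The comparison is an adherence description: units transfused is not a primary, secondary or tertiary aim and plays no part in alpha spending. The SAP also shows the whole distribution, models hemoglobin separation with intervals, and counts departures from the assigned strategy. All of this stands, and it is why the point is minor.

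A reader might go further than the documents allow in two ways.

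- **That units given in sequence within a patient make the reported significance wrong.** Dependence within a patient matters only through the variance of the patient-level count, and the documents do not give that variance. The two arms' departures can nearly cancel, as in the geometric case of step 2 (3.11 against 3.20). That cancellation would be luck; nothing in the plan ensures it.
- **That every liberal patient receives the protocol unit.** The SAP itself plans to count liberal patients with no transfusion, and it allows delays, so some zeros are expected there too.

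The reply does not justify keeping the test. A method whose variance assumption is doubtful under the trial's own rules has no advantage over one that estimates the variance.

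**Conclusion.** The concern holds as a minor point. The simple Poisson test rests on variance equal to the mean, the transfusion rules make that doubtful in both arms, and no safeguard is specified. Its p-value may be too small or too large. For an assumed overall variance/mean ratio of 0.5 to 3, the true size of a nominal 5% test is about 0.6% to 26%. An interval from the same model would be affected in the same way, but the SAP does not currently promise one.

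It would be wrong to infer that significance will be overstated, or that the evidence of separation in blood use is unsafe. The first depends on a dispersion the documents do not report, and the second fails at any separation near the 1.22 units cited from other trials. No efficacy or safety conclusion rests on this test. The assumptions are φ, the mean units in each arm and every input to the give-to-target simulation.

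**What to change.** In SAP section 6, Adherence to Assigned Intervention, replace the simple Poisson test with the difference in mean units per patient (Restrictive minus Liberal) and a 95% CI from an unequal-variance or bootstrap standard error. Take the p-value from that same comparison; Poisson regression with robust variance is an acceptable alternative. Note the change from Protocol F4 4.b.

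The Wilcoxon test that the SAP uses for length of stay should not supply the p-value here. It does not test the difference in means, so it could disagree with the interval printed beside it.

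The cost is one sentence. The change needs no new data and does not affect alpha or the power of the primary comparison.

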Restrictive Transfusion Strategy: Patients randomized to the restrictive transfusion strategy will be permitted to receive a transfusion if the hemoglobin concentration falls below 8 g/dL and will be strongly recommended to receive transfusion if the hemoglobin concentration is below 7 g/dL. Transfusion is also permitted if angina symptoms (i.e., retrosternal chest discomfort, chest discomfort described as pressure or heaviness) that are thought by the clinician to be related to anemia occur and are not controlled with anti-anginal medications (sublingual nitroglycerin or equivalent therapy). Blood will be administered one unit at a time and enough blood given to increase the hemoglobin concentration above 7 to 8 g/dL or to relieve symptoms of uncontrolled angina.

Liberal Transfusion Strategy: Patients randomly allocated to the liberal transfusion strategy will receive one unit of packed red cells following randomization and will receive enough blood to raise the hemoglobin concentration to 10 g/dL or above any time the hemoglobin concentration is detected to be below 10 g/dL. A post transfusion hemoglobin measurement showing a hemoglobin level of at least 10 g/dL must be obtained.

A patient in either group may be transfused at any time without a hemoglobin level if the patient is actively bleeding (e.g., brisk gastrointestinal bleeding) and the physician believes an emergency transfusion is needed. A patient in either group with history of congestive heart failure or low ejection fraction may receive diuretics prior to or after transfusion.

3.c Rationale for Transfusion Thresholds

The restrictive transfusion group reflects many current guidelines (including European guidelines)(51, 61). A blood transfusion will be permitted in the restrictive group if the hemoglobin concentration is less than 8 g/dL. Discussions with many cardiologists suggested that many clinicians are not

comfortable with a threshold as low as 7 g/dL (as used in TRICC); however, individual clinicians may choose to use a threshold of less than 7 g/dL to trigger transfusions. Patients may be transfused for signs or symptoms when the clinician believes it is necessary although this did not occur in the pilot trial and was uncommon in the FOCUS trial which also incorporated symptoms in the restrictive transfusion protocol.

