The clinical site is to obtain a daily hemoglobin level for each randomized patient for the first three days following randomization (or through hospital discharge, if sooner). Additional hemoglobin levels are measured as clinically indicated. Study staff will closely monitor each patient to ensure that each of the required hemoglobin levels are drawn, review the results, and confirm that the transfusions have been ordered (or not ordered) in accordance with the transfusion assignment. If there is a hemoglobin value that should trigger a transfusion and none is ordered or, as the alternative, a transfusion ordered without a hemoglobin value to trigger the transfusion, study staff will discuss the case with the treating physician. Likewise, if a required hemoglobin level has not been ordered, the study staff will alert the physician. The required hemoglobin measurements are of primary importance to verify that patients in the liberal strategy maintain a level of at least 10 g/dL.

The clinical site will also request assistance from the blood bank to help prevent protocol violations in the restrictive strategy. Study staff will notify the blood bank each time a patient is assigned to the restrictive strategy and request notification prior to the release of any red blood cell transfusions that are ordered. The study staff will then review the medical record to verify that the transfusion is in accordance with the protocol. If administration of blood is a violation of the protocol, study staff will contact the ordering physician to discuss transfusion plans and to clarify the study protocol. However, study staff do not approve or disapprove the transfusion. The final decision on the transfusion is always the treating physician's.

Study wide, the DCC will centrally monitor transfusions and hemoglobin levels on an ongoing basis. Transfusion rates for each strategy will be measured overall and by clinical site. Specifically, the DCC will identify instances when 1) patients randomized to the liberal strategy do not receive a transfusion, 2) patients randomized to the liberal strategy are discharged with a hemoglobin level < 10 g/dL and, 3) patients randomized to the restrictive strategy without anginal symptoms and a hemoglobin level \geq 8 g/dL receive a transfusion. Reports of the protocol violations will be prepared by the DCC. The Clinical Coordinating Center (CCC) will review these reports and discuss as necessary with the clinical sites.

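### The SAP's restrictive-arm transfusion count omits transfusions at exactly 8.0 g/dL and does not formally separate permitted transfusions from deviations

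*SAP*

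**What the plan says.** **The rule.** SAP section 1, Trial Transfusion Strategies, states that restrictive patients "may receive a transfusion if the hemoglobin concentration falls below 8 g/dL". Protocol D3 3.b gives the same trigger. Both documents also allow transfusion for anemia-related angina that medication does not control. Both state that a patient in either group "may be transfused at any time without a hemoglobin level if the patient is actively bleeding" and the physician judges an emergency transfusion necessary. The SAP alone adds: "The transfusion protocol is suspended for 24 hours if the patient goes to surgery". It also has a sentence on transfusion during dialysis that the protocol lacks.

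**The protocol's check.** Protocol D3 3.f has the data center identify "patients randomized to the restrictive strategy without anginal symptoms and a hemoglobin level" of 8 g/dL or above who are transfused.

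**The SAP's count.** Adherence to Assigned Intervention (SAP section 6) reports "the number (%) of randomized patients with at least one transfusion given when" hemoglobin is above 8. Separately it reports "the number (%) of patients with at least one transfusion when no hemoglobin level was checked". It then adds: "Clinical reasons will be provided when possible".

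**The concern.** The SAP count and the protocol check address the same question, whether a restrictive patient was transfused outside the rule, but they differ in two ways.

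First, the boundary has moved. With a trigger of below 8, a value of exactly 8.0 is outside it, and the protocol check treats it so. The SAP's strict inequality does not.

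Second, the protocol check sets aside patients with anginal symptoms, while the SAP count sets aside nobody. Its companion count of transfusions without a level likewise makes no allowance for active bleeding, which both documents permit.

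What is at stake is the accuracy of a published description of protocol adherence, and its agreement with the violation reports prepared during the trial. The SAP also tests non-inferiority of the restrictive strategy, and readers of such a result will want to know how often that arm was transfused outside its rule.

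**Working it through.** No adherence figure is stated in either document, so there is nothing to reproduce. The check is a comparison of rules, followed by a statement of what can and cannot be sized.

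**1. Rules side by side (restrictive arm)**

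| Transfusion given | Under the strategy | Protocol 3.f check | SAP count |
|---|---|---|---|
| Below 8 g/dL | Permitted | Not flagged | Not counted |
| Exactly 8.0, no permitted reason, no angina | Outside the trigger | Flagged | Not counted |
| Above 8, no permitted reason, no angina | Outside the trigger | Flagged | Counted |
| Above 8, uncontrolled anemia-related angina | Permitted | Not flagged | Counted |
| Above 8, no angina, within the 24-hour surgical suspension | Rule suspended (SAP only) | Flagged | Counted |
| No level, active bleeding, emergency | Permitted | Not flagged (no level to test) | Counted in the no-level count |

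The second row is the omission. The last three rows are transfusions that SAP section 1 allows but the SAP counts include.

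**2. Direction of the effect on the above-8 count.** Let

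- T = share of restrictive patients with at least one transfusion at 8.0 or above and no permitted reason;
- x = share with such a transfusion at exactly 8.0 and no transfusion of any kind above 8;
- y = share with no such transfusion but at least one permitted transfusion above 8.

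Then the reported share is R = T − x + y. The boundary lowers R, the missing separation raises it, and the two cancel when x = y. The no-level count has only the upward component.

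**3. Illustration, on assumed values only.** With 3500 patients allocated 1:1, the restrictive arm has about 3500 / 2 = 1750. Assume T = 10%, with x and y each between 0 and 5%.

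- x = 5%, y = 0: R = 10 − 5 + 0 = 5%, which is 0.05 × 1750 ≈ 88 patients too few.
- x = 0, y = 5%: R = 10 − 0 + 5 = 15%, about 88 too many.
- x = 1%, y = 3%: R = 10 − 1 + 3 = 12%, which is 0.02 × 1750 = 35 too many.

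Neither x nor y is given in the documents, so this shows direction and scale only.

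**4. Why the omission cannot be sized.** Suppose hemoglobin is reported to 0.1 g/dL. If off-trigger transfusions were spread evenly over 8.0–8.9, then 1/10 = 10% would fall at exactly 8.0. Over 8.0–9.9 it would be 1/20 = 5%. If their frequency halved every h g/dL above the threshold, the share would be 1 − 2^(−0.1/h), which is 29% for h = 0.2 and 13% for h = 0.5. The answer depends on an assumed shape. These are also shares of transfusions, whereas the SAP counts patients with at least one: someone transfused at 8.0 and again above 8 is still counted.

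**5. Permitted-reason wording.** Protocol 3.b names uncontrolled angina related to anemia. Protocol 3.c says "Patients may be transfused for signs or symptoms when the clinician believes it is necessary", which is wider. Protocol 3.f excepts anginal symptoms without the two qualifiers in 3.b. The surgery and dialysis provisions appear only in the SAP. A programmer cannot classify a transfusion as permitted until these are reconciled.

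**The case against.** The strongest reply is that the SAP presents plain descriptive counts, shown openly with reasons, and does not call each counted patient a violator. Much of this stands. The SAP combines nothing into a single adherence rate, so a reader who infers that a reported rate is wrong in both directions goes further than the text allows. The reasons do let a reader separate some permitted transfusions, although the qualifier leaves the separation incomplete and no rule for it is given. Protocol 3.c also says that symptom-triggered transfusion did not occur in the pilot and was uncommon in an earlier trial with a similar provision, which limits that part of the over-count.

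Other tempting inferences also fail:

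- **That these counts decide whether the per-protocol analysis is run.** SAP Primary Outcome Analysis makes that analysis conditional on adherence being a concern, but sets no threshold and does not refer to these counts.
- **That treatment separation is mismeasured.** Separation is described by units transfused and by the day 1–3 hemoglobin model, neither of which depends on the 8.0 boundary.
- **That all the SAP's exceptions are missing from Protocol D3.** Angina and active bleeding are both in 3.b; only surgery and dialysis are absent.
- **That the dialysis sentence permits transfusion above 8.** It follows text on delaying transfusion for volume reasons and may concern timing only.

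The protocol check is not a perfect benchmark either, since angina is its only stated exception.

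None of this reaches the boundary mismatch. A lost symbol in the PDF reading is an unlikely explanation, because greater-than-or-equal signs survive elsewhere in the SAP, for example in Subgroup Analyses.

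**Conclusion.** The point holds as a minor correction. Followed literally, the SAP leaves out patients whose only off-trigger transfusions were at exactly 8.0 and who are flagged under Protocol 3.f if they had no anginal symptoms. Its restrictive-arm counts also combine permitted transfusions with deviations, separated only by reasons where available. The two features act in opposite directions on the above-8 count, and neither the size nor the sign of the net effect can be fixed from the documents. The illustrative figures rest entirely on assumed shares. The primary analysis is by intention to treat and is unaffected. The only analysis of outcomes that could be touched is the conditional per-protocol sensitivity analysis, and only if the same counts were used to define its population, which the SAP does not say.

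**What to change.** 1. In SAP Adherence to Assigned Intervention, change the restrictive-arm cut-off from above 8 to 8 g/dL or above, to match Protocol D3 3.f. This alone removes the omission but not the mixing.
2. Within each restrictive-arm count, tabulate three groups: transfusions with a recorded permitted reason, those with no such reason, and those with reason unknown. Do not treat unknown as a deviation.
3. If the per-protocol sensitivity analysis is run, state that it uses the same classification.
4. Reconcile the permitted-reason wording across Protocol D3 3.b, 3.c and 3.f and SAP section 1, including the surgery and dialysis provisions. Which clinical rule is right is for the investigators; this review takes no position.

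The cost is SAP wording and a small programming change. In-hospital hemoglobin values are already collected. A reason for every transfusion may not be: Protocol E8 and Appendix 2 list the number, timing and unit details of transfusions but no reason for each, so the unknown group may not be empty. The reported counts may move slightly.
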